8.1.2 Treatment Groups

The study population will consist of patients of either sex, aged between 21 and 80 years (both inclusive) that have tested positive for SARS-CoV-2 by Reverse Transcriptase -Polymerase Chain Reaction (RT-PCR) assay using a respiratory tract sample (nasopharyngeal swab or oropharyngeal swab or nasal aspirate or tracheobronchial aspirate) and clinically assessed to have moderate to severe COVID-19. The study will be conducted in the Arabian Gulf region. An adequate number of patients will be screened in order to randomize 780 patients into two treatment groups at a 1:1 ratio, so as to have approximately 390 patients in favipiravir + supportive care group and 390 patients in placebo + supportive care group.

8.2 Efficacy endpoints

Stage I

Primary Efficacy Endpoint:

Time to resolution of hypoxia (Time frame: Up to 28 days)

This endpoint will be considered to have been met when the patient has attained a score of 4 or lower on the 10-point ordinal scale of clinical status and either of a) or b), and c) is met:

- a) Score is ≤ 4 on consecutive assessments over the next 5 days, if patient continues to remain in hospital (i.e., has not been discharged).

OR

- b) Patient was discharged before five consecutive assessments (after reaching a score of 4).

AND

- c) The patient has survived and has not been re-admitted to hospital for COVID-19 management through Day 28.

*Note: Part c) is applicable to patients in both a) and b)
 i.e. Time to resolution of Hypoxia = either "a and c" OR "b and c" is met.*

Secondary Efficacy Endpoints:

1. Time to discharge from hospital.
2. Time (no. of days) from randomization to the earliest time when **ALL** COVID-19 associated symptoms (fever, chills, cough, sore throat, malaise, headache, muscle pain, gastrointestinal symptoms – specifically diarrhoea and vomiting, shortness of breath or dyspnoea) are scored by the Investigator/trained study personnel as either '0=absent' or 'mild=1' in assessments over a period of 24 hours, when assessed from baseline to Day 28 or discharge from hospital (if discharge happens earlier than Day 28).

Statistical Analysis Plan
Sponsor: [name], Inc

Study Number: NV-05-983-2020

Version: 2.0 Date: 06JAN2021

3. Percentage of patients with score of either '0=absent' or 'mild =1' over a period of 24 hours, for **ALL** COVID-19 associated symptoms, by Days 4, 7, 10 14, 21 and 28 or discharge (if discharge happens earlier than one or more of the above-mentioned time points)

Note: Symptoms evaluated are fever, chills, cough, sore throat, malaise, headache, muscle pain, gastrointestinal symptoms- specifically, diarrhoea and vomiting, shortness of breath or dyspnoea. The Investigator/trained study personnel will assess (including by enquiry with the patient, as necessary) and score the severity of each COVID-19 associated symptom on a 5 point Likert-type scale (0= absent, 1= mild, 2=moderate, 3= severe, 4= very severe/critical).

4. Time to improvement in **EACH** of the symptoms of fever, chills, cough, sore throat, malaise, headache, muscle pain, gastrointestinal symptoms- specifically diarrhoea and vomiting, shortness of breath or dyspnoea by at least 1 grade over baseline.

Note: Severity of symptoms will be evaluated once daily (preferably at or around the same clock time) on each day that the patient is admitted in the hospital. The Investigator/trained study personnel will assess (including by enquiry with the patient, as necessary) and score the severity of each COVID-19 associated symptom on a 5-point Likert-type scale (0= absent, 1= mild, 2=moderate, 3= severe, 4= very severe/critical). The improvement observed must be sustained at evaluations over a period of 24 hours, in order for this secondary efficacy endpoint to be reached.

5. Percentage of patients reporting a clinical relapse of COVID-19 when assessed from day of discharge to 27 days after randomization (Day 28).

Note: 'Clinical relapse' is defined as either the reappearance or worsening of severity (over the assessment on the day of discharge) of one or more of the above-mentioned COVID-19 associated symptoms, or the appearance of any of these symptoms (due to COVID-19 infection) for the first time after discharge. This endpoint will be assessed only for those patients that were discharged before Day 28.

6. Time (no. of days) to negative conversion of detectable SARS-CoV-2 viral RNA in the RT-PCR assays of respiratory sample, from randomization.

7. Percentage of patients showing negative conversion of detectable SARS-CoV-2 viral RNA in the RT-PCR assays of respiratory samples on Days 5, 10 and 28 or discharge (if discharge happens earlier than one or more of the above-mentioned time points)

8. Changes over time in patient's clinical status on the 10-point ordinal scale used in the SOLIDARITY trial by WHO

Statistical Analysis Plan
Sponsor: [name], Inc

Study Number: NV-05-983-2020

Version: 2.0 Date: 06JAN2021

- a. Changes in the 10-point ordinal scale score from baseline until discharge
 - b. Proportion of patients in whom clinical status score of 4 ('hospitalized, no oxygen required') or lower has been attained by Days 4, 7, 10, 14, 21 and 28 or discharge (if discharge happens earlier than one or more of the above-mentioned time points)
 - c. Time (no. of days) from randomization to clinical status score improvement by 1 and by 2 points (from baseline)
 - d. Proportion of patients for whom clinical status score improvement by 1 and by 2 points has been attained by Days 4, 7, 10, 14, 21 and 28 or discharge (if discharge happens earlier than one or more of the above-mentioned time points)
9. Changes over time in patient's clinical status on the 8-point ordinal scale
- a. Time (no. of days) from randomization to attain clinical status score of 4 or lower
 - b. Proportion of patients in whom clinical status score of 4 or lower has been attained by Days 4, 7, 10, 14, 21 and 28 or discharge (if discharge happens earlier than one or more of the above-mentioned time points)
 - c. Time (no. of days) from randomization to attain clinical status score of 3 or lower
 - d. Proportion of patients in whom clinical status score of 3 or lower has been attained by Days 4, 7, 10, 14, 21 and 28 or discharge (if discharge happens earlier than one or more of the above-mentioned time points)
 - e. Time (no. of days) from randomization to clinical status score improvement by 1 and by 2 points (from baseline)
 - f. Proportion of patients for whom clinical status score improvement by 1 and by 2 points has been attained by Days 4, 7, 10, 14, 21 and 28 or discharge (if discharge happens earlier than one or more of the above-mentioned time points)
10. Changes over time in findings on chest X-ray
11. Changes over time in the National Early Warning Score-2 (NEWS)
12. Percentage of patients requiring, until Day 28 or discharge from hospital (if discharge happens earlier)
- a. Management in intensive care unit
 - b. High Flow Nasal Oxygen or Non-invasive mechanical ventilation
 - c. Invasive mechanical ventilation
13. Time (no. of days) from randomization to:
- a. Management in intensive care unit

Statistical Analysis Plan
Sponsor: [name], Inc

Study Number: NV-05-983-2020

Version: 2.0 Date: 06JAN2021

- b. High Flow Nasal Oxygen or Non-invasive mechanical ventilation
- c. Invasive mechanical ventilation

over an assessment period from randomization until Day 28 or discharge from hospital (if discharge happens earlier)

14. Duration (no. of days) the patient requires:

- a. Management in intensive care unit
- b. Oxygen supplementation
- c. High Flow Nasal Oxygen
- d. Non-invasive mechanical ventilation
- e. Invasive mechanical ventilation

over an assessment period from randomization until Day 28 or discharge from hospital (if discharge happens earlier)

15. Percentage of patients:

- a. dying from any cause
- b. dying from a COVID-19 associated complication

Over an assessment period from randomization until Day 28 or discharge from hospital (if discharge happens earlier).

Stage II

- 1. Percentage of patients reporting a clinical relapse of COVID-19 when assessed from day of discharge to 59 days after randomization (Day 60).

Note: 'Clinical relapse' is defined as either the reappearance or worsening of severity (over the assessment on the day of discharge) of one or more of the above-mentioned COVID-19 associated symptoms, or the appearance of any of these symptoms (due to COVID 19 infection) for the first time after discharge.

- 2. Proportion of patients
 - a. with disease worsening and requires:
 - i. Admission to ICU
 - ii. High flow nasal oxygen
 - iii. Non-invasive mechanical ventilation
 - iv. Invasive mechanical ventilation

(AND)

	Statistical Analysis Plan Sponsor: [name], Inc	
	Study Number: NV-05-983-2020	Version: 2.0 Date: 06JAN2021

- b. Dying
until day 60 (regardless of whether patients are discharged from hospital before Day 28 or not)

8.3 Safety Endpoints

Safety endpoint will be as follows:

Stage I

1. Number (and percentage) of patients reporting treatment emergent adverse events (TEAEs) (by MedDRA system organ class and preferred term)
2. Changes of parameters at each assessment during the study/follow-up period, compared to baseline for:
 - Vital signs: body temperature, heart rate, respiratory rate, systolic/diastolic blood pressure (BP) and oxygen saturation.
 - Clinical laboratory assessments: hematology, serum chemistry, urinalysis.
 - 12-lead ECG: Changes in heart rate, PR, QRS, QT and QT_B intervals.

Stage II

1. Number (and percentage) of patients reporting treatment emergent adverse events (TEAEs) (by MedDRA system organ class and preferred term)

9 General Statistical Considerations

9.1 Descriptive Statistics

The following descriptive statistics will be calculated for continuous data and for ordered categorical data (ordinal data):

Summary statistics are displayed with the following digits:

Description	Characteristic	Number of decimal places
Count	n	0
Count corresponding to the number of patients for a group	N	0
Mean	Mean	As in source + 1
Standard Deviation	SD	Mean+1
Minimum	Min	As in source
Median	Median	As in source + 1
Maximum	Max	As in source
Quartile 1	Q1	As in source+1

	Statistical Analysis Plan Sponsor: [name], Inc	
	Study Number: NV-05-983-2020	Version: 2.0 Date: 06JAN2021

Description	Characteristic	Number of decimal places
Quartile 3	Q3	As in source+1
Inter Quartile Range	IQR	As in source+1
Percentage relative to N #	%	1

Number of decimal places can be more than one, if necessary. All table percentages should be rounded to one decimal place if not stated otherwise.

All data will be presented in the subject data listings.

If either table or listing does not include any observation, then the following placeholder will be used: "NO DATA CONTRIBUTED TO THIS TABLE / LISTING".

9.2 Analysis Population

Four analysis populations will be considered as defined below:

Analysis Population	Definition
Screened Population	All participants who signed the informed consent form
Safety Population (SAF)	All randomized patients who received at least one dose of the study medication
Intention-to-treat (ITT)	All randomized patients who received at least one dose of the study medication
Modified Intention to treat (mITT)	All randomized patients who received at least one dose of the study medication and has at least one post dose primary efficacy endpoint assessment available. (Note: if there is a greater than 5% difference in the number of patients in the ITT and mITT populations, then analysis for mITT population will be provided additionally.)
Per protocol set (PPS)	All patients included in the ITT who complete the study without major protocol deviation which would affect the primary endpoint of the study.

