11 STATISTICAL METHODS

11.1 Analysis Sets

Four Analysis populations will be considered for this study which are defined as below.

Screened Population: All participants who signed the informed consent form.

Safety Population (SAF): All randomized patients who received at least one dose of the study medication.

Intention-to-treat (ITT): All randomized patients who received at least one dose of the study medication.

Modified Intention to treat (mITT): All randomized patients who received at least one dose of the study medication and has at least one post dose primary efficacy endpoint assessment available.

(Note: If there is a greater than 5% difference in the number of patients in the ITT and mITT populations, then analyses for mITT population will be provided additionally)

Per protocol set (PPS): All patients included in the ITT who complete the study without major protocol deviation which would affect the primary endpoint of the study.

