11.2 General Statistical Considerations

Adverse events and medical history will be classified using standard Medical Dictionary for Regulatory Activities (MedDRA Version 23.0) terminology. Prior and concomitant medications (including medications which are a part of supportive care) will be coded with the World Health Organization Drug Global (WHO-DG, version March 1, 2020) dictionary as applicable.

Unless otherwise specified, the primary efficacy analysis will be done using ITT population. The statistical significance level is 0.05 by one sided or two-sided test, wherever appropriate. Mean/Median estimate (and other general statistics such as Inter quartile range, SD, min, max) and the 95% CI for the estimates of the mean will be provided for the applicable efficacy endpoint. Endpoints will be analysed descriptively and inferentially wherever necessary. Details of the statistical methods will be described in the SAP, which will be finalized before study database lock of Stage I of the study.

Description of statistics:

The primary indicators collected in this study will be described by appropriate statistical methods. To briefly mention, Quantitative indicators will be described by arithmetic mean, standard deviation, median, inter quartile range, maximum, minimum etc.; qualitative indicators will be described by frequency and percentage.

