40 document is being implemented immediately, but it remains subject to comment in accordance
41 with the Agency's good guidance practices.

42
43 In general, FDA's guidance documents, including this guidance, do not establish legally
44 enforceable responsibilities. Instead, guidances describe the Agency's current thinking on a
45 topic and should be viewed only as recommendations, unless specific regulatory or statutory
46 requirements are cited. The use of the word *should* in Agency guidance means that something
47 is suggested or recommended, but not required.

48 49 50 **II. BACKGROUND**

51
52 There is currently an outbreak of respiratory disease caused by a novel coronavirus. The virus
53 has been named SARS-CoV-2 and the disease it causes has been named Coronavirus Disease
54 2019 (COVID-19). On January 31, 2020, HHS issued a declaration of a public health
55 emergency related to COVID-19, effective January 27, 2020, and mobilized the Operating
56 Divisions of HHS.⁵ In addition, on March 13, 2020, the President declared a national
57 emergency in response to COVID-19.⁶

58
59 COVID-19 can range from mild to severe disease, the latter including pneumonia, severe acute
60 respiratory syndrome, multi-organ failure, and death. The incubation period for SARS-CoV-2 is
61 thought to be as long as 14 days, with a median time of 4 to 5 days from exposure to symptom
62 onset.⁷ There are currently no FDA-approved drugs to treat COVID-19. Clinical management
63 includes symptomatic and supportive care, such as supplemental oxygen, mechanical ventilation,
64 and extracorporeal membrane oxygenation (ECMO) when indicated.

65

⁵ Secretary of Health and Human Services Alex M. Azar, Determination that a Public Health Emergency Exists. (Jan. 31, 2020, renewed April 21, 2020), available at <https://www.phe.gov/emergency/news/healthactions/phe/Pages/default.aspx>.

⁶ Proclamation on Declaring a National Emergency Concerning the Novel Coronavirus Disease (COVID-19) Outbreak (March 13, 2020), available at <https://www.whitehouse.gov/presidential-actions/proclamation-declaring-national-emergency-concerning-novel-coronavirus-disease-covid-19-outbreak/>.

⁷ See the Centers for Disease Control and Prevention Interim Clinical Guidance for Management of Patients with Confirmed Coronavirus Disease (COVID-19), available at <https://www.cdc.gov/coronavirus/2019-ncov/hcp/clinical-guidance-management-patients.html>.

Contains Nonbinding Recommendations

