 361 grading scales include those published by the National Institutes of Health's Division of
 362 AIDS²⁵ and the National Cancer Institute (NCI).²⁶

363

364 • Sponsors should address the potential for drug-drug interactions that could increase the
 365 risk for toxicities (caused by increased exposures of the drug or the drug that it interacts
 366 with) and propose mitigation strategies.

367

²⁵ See the National Institutes of Health's Division of AIDS Adverse Event Grading Tables, available at <https://rsc.niaid.nih.gov/clinical-research-sites/daids-adverse-event-grading-tables>.

²⁶ See the National Cancer Institute's Common Terminology Criteria for Adverse Events, available at https://ctep.cancer.gov/protocolDevelopment/electronic_applications/ctc.htm.

Contains Nonbinding Recommendations

368 • Safety assessments (e.g., vital signs, laboratory studies, electrocardiograms) should be
 369 performed on a schedule commensurate with severity of illness and the identified
 370 potential risk of the study drug.

371
 372 • Sponsors should conduct safety reporting as outlined in FDA regulations²⁷ and relevant
 373 guidance.²⁸

374 **E. Statistical Considerations**

375
 376 Sponsors of drugs to treat or prevent COVID-19 should consider the following statistical
 377 considerations:
 378

- 379
- 380 • The primary efficacy analysis should be conducted in an intention-to-treat population,
 381 defined as all randomized subjects.
 - 382
 - 383 • The primary efficacy analysis should be prespecified in the protocol.
 - 384
 - 385 • To the extent possible, sponsors should justify their assumptions in sample size
 386 calculations. The sample size should be large enough to provide a reliable answer to the
 387 safety and efficacy questions the trial is meant to address.
 - 388
 - 389 • Examples of analytic approaches for the primary efficacy analysis include:
 390
 - 391 – Binary outcome analysis: each person is classified as having a successful or an
 392 unsuccessful outcome, with a difference in proportions used to compare treatment
 393 arms.
 - 394
 - 395 – Ordinal outcome analysis: options include a proportional odds approach, a rank-based
 396 approach, and an approach to compare means with a score or weight assigned to each
 397 category. Any of these approaches should be supplemented by analyses
 398 communicating how treatment impacts different categories of the scale.
 - 399

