Necessary steps will be taken to properly manage the situation of informative censoring for patients who did not reach the resolution of hypoxia endpoint. For censored patients who died of any cause, discontinued or were lost to follow-up due to treatment-related adverse events or lack of efficacy, they will be censored at Day 28. However, censored patients who discontinued or were lost to follow-up for reasons that were independent of the study medication will be censored at the day of discontinuation of lost to follow-up. Censored patients who were still in the study follow-up at the time of the analysis will be censored at the last day of available follow-up data.

The above primary endpoint analysis will be done using ITT population

Also, the primary efficacy analysis will be repeated using PP population.

Sensitivity analysis for primary endpoint [12](#):

Three sensitivity analyses are planned.

1. The first is a more relaxed definition of time to resolution of hypoxia. In this analysis, the resolution of hypoxia is defined if subject's clinical status score ≤ 4 is maintained for two consecutive days. The timing of the resolution event will still be the first day when the score falls to 4 or lower. This sensitivity analysis will be done using ITT as described in the primary endpoint.

Statistical Analysis Plan
Sponsor: [name], Inc

Study Number: NV-05-983-2020

Version: 2.0 Date: 06JAN2021

2. The second sensitivity analysis will be based on Kaplan-Meier estimates and log-rank test. Median time to event, along with standard error, percentage of patients achieved resolution of hypoxia, percentage of patients censored, and two-sided p-value obtained using log-rank test at 5% level of significance will be presented for observed case using ITT population.
3. The third sensitivity analysis will be a worst-rank analysis proposed by Lachin (1999). The two treatment groups will be compared by a Wilcoxon-Mann-Whitney test as implemented in SAS PROC NPAR1WAY. Tied ranks will be assigned the midrank. The ranks will be determined as follows:
 - 1) The lowest (best) ranks will be given to patients who meet the primary endpoint definition of treatment success, beginning with the earliest treatment success after beginning of treatment, and survive to Day 28.

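### The set labelled ITT requires at least one dose and is the same as the Safety set, so no planned efficacy analysis covers all randomized patients

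*SAP*

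**What the plan says.** Protocol 11.1 gives two sets the same content: "Safety Population (SAF): All randomized patients who received at least one dose of the study medication" and "Intention-to-treat (ITT): All randomized patients who received at least one dose of the study medication". The table in SAP 9.2 repeats this, with "All randomized patients who received at least one dose of the study medication" as the entry for both.

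The primary analysis is tied to that set in both documents. Protocol 11.2 says that "the primary efficacy analysis will be done using ITT population", and SAP 10.6.1 says "The above primary endpoint analysis will be done using ITT population", with a repeat in the per-protocol set. The three sensitivity analyses, the secondary analyses and the subgroup analyses also use ITT. The interim efficacy analysis follows SAP 10.6.1. The mITT and per-protocol sets are subsets of ITT.

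Protocol Appendix I reproduces regulatory guidance on COVID-19 trials. Its statistical section says "The primary efficacy analysis should be conducted in an intention-to-treat population", "defined as all randomized subjects". Its introduction states that guidance documents "should be viewed only as recommendations, unless specific regulatory or statutory" requirements are cited.

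**The concern.** Receiving a dose happens after randomization. Restricting the confirmatory comparison to dosed patients gives up part of the balance that randomization provides, and the plan names no benefit in return. If the undosed patients differ in prognosis, or differ in number between arms, the primary hazard ratio is affected and no other planned efficacy analysis would show it.

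The label matters as well. The report would describe as ITT an analysis that the protocol's own appendix would not call ITT. The set called mITT narrows it further. Its 5% trigger compares two sets that both exclude undosed patients, so it cannot reveal how many were left out.

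**Working it through.** **1. Comparing the definitions**

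| Set | Condition | Source |
|---|---|---|
| Safety | randomized and dosed | Protocol 11.1, SAP 9.2 |
| ITT | randomized and dosed | Protocol 11.1, SAP 9.2 |
| mITT | ITT plus a post-dose primary endpoint assessment | Protocol 11.1, SAP 9.2 |
| Per protocol | ITT, completed, no relevant major deviation | Protocol 11.1, SAP 9.2 |
| ITT in the guidance | randomized | Protocol Appendix I |

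No efficacy set in the plan matches the last row.

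**2. Reproducing the plan's sample size** (SAP 9.6: HR 1.25, two-sided 0.05, 80% power, event probabilities 0.9 and 0.8)

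- Events (Schoenfeld) = 4 × (1.960 + 0.842)² / (ln 1.25)² = 631, as stated.
- Evaluable patients = 631 / 0.85 = 742.4, against 742 stated.
- Inflation for 5% dropout: 371 / 0.95 gives 391 per arm and 371 × 1.05 gives 390. The plan has 390, a trivial difference.

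The plan's figures stand. This point disputes none of them.

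**3. Power if all randomized patients are analysed**

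780 × 0.85 = 663 events. Power = Φ(√663 / 2 × ln 1.25 − 1.960) = 0.819 with nobody undosed. The documents give no undosed rate, so the fraction u is an assumption. Undosed patients are taken to have no treatment effect, approximated as log HR × (1 − u), with no other loss. For the dosed-only set, events fall to 663 × (1 − u) at HR 1.25.

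| u | undosed of 780 | diluted HR | power, all randomized | power, dosed only |
|---|---|---|---|---|
| 0.5% | about 4 | 1.249 | 0.816 | 0.817 |
| 1% | about 8 | 1.247 | 0.812 | 0.816 |
| 2% | about 16 | 1.244 | 0.804 | 0.812 |
| 5% | 39 | 1.236 | 0.779 | 0.800 |

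These use the 0.05 level of SAP 9.6. At the final-look level of 0.04521 in SAP Appendix I (critical value 2.0027) the same formula gives 0.800 and 0.792 for all randomized patients at u = 1% and 2%, against 0.804 and 0.800 for dosed only. The cost of including everyone is thus below one percentage point at either level.

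**4. An extreme case for bias**

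Assumptions: 390 per arm, constant hazards, control resolution 0.8 by Day 28, HR 1.25. Eight patients unresolved at Day 28 are dropped from one arm only.

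- Control hazard = −ln(0.2) / 28 = 0.0575 per day. Events = 390 × 0.8 = 312. Person-time = 312 / 0.0575, about 5,428 days.
- Favipiravir hazard = 1.25 × 0.0575 = 0.0718 per day. Event probability = 1 − 0.2^1.25 = 0.866. Events about 338. Person-time about 4,702 days.
- The eight dropped patients carry 8 × 28 = 224 days and no events.
- Dropped from placebo: shift = −ln(1 − 224 / 5,428) = 0.042, lowering the HR.
- Dropped from favipiravir: shift = −ln(1 − 224 / 4,702) = 0.049, raising the HR.
- SE of log HR = √(1/312 + 1/338) = 0.079. The shifts are 0.54 and 0.62 SE.

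Simulated Cox fits under the same assumptions agree: about 0.04 and 0.05. Taking 8 / 390 = 2% as the shift would understate it, because a patient unresolved at Day 28 stays at risk throughout and carries more than an average share of person-time.

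**5. Whether changing the definition alone is enough**

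It is not. SAP 9.3 ties Baseline to the first dose, and the primary Cox model uses the baseline ordinal score as a covariate, so an undosed patient has no defined covariate value. Protocol 11.4.1 starts the clock at first administration, while SAP 9.3 starts it at randomization; an undosed patient has no first-dose date. Under SAP 10.6.1, an undosed patient who leaves for reasons independent of the medication is censored on the day of leaving. If that is Day 1, the patient adds essentially no information.

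**The case against.** The strongest reply is that very few patients should be affected and that exclusion should not depend on arm. Protocol 6.1.2 places the eligibility check, randomization and first dose at the same Day 1 visit, which leaves little time to deteriorate or withdraw. Protocol 5.1.6 blinds patients, investigators, site staff and the sponsor, and the placebo matches. A footnote to Table 1 of Protocol 5.1 also lets patients who become ventilated during the study be dosed by tube, so intubation does not by itself make a patient undosed. The disposition table in SAP 10.1 will report how many were randomized and how many were dosed. All of this stands, and it limits the expected bias. It does not justify the definition: if the excluded patients are few, including them costs almost nothing.

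Three stronger readings are not supported. A reader might infer that the plan breaches a requirement or contradicts itself. The guidance is nonbinding, and the protocol body invokes it for severity and critical-illness definitions without committing to its statistical section, so this is an unexplained departure from a recommendation. A reader might infer that the undosed will be poor-prognosis patients. That is possible, but nothing in the documents shows it. And a reader might take the extreme case above as an expected bias. It needs all eight exclusions to be non-resolvers in the same arm, which blinding makes unlikely.

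**Conclusion.** The point holds. The primary analysis labelled ITT is a modified ITT restricted to dosed patients, the set coincides with the Safety set, and no planned efficacy analysis covers everyone randomized. The SAP and protocol agree with each other here, so both need the change.

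The expected effect on the hazard ratio is small. The upper illustration of 0.04 to 0.05 on the log scale (0.5 to 0.65 SE) rests on constant hazards, 80% control resolution, HR 1.25 and eight one-sided exclusions. The 1 to 2% undosed rate behind the power figures is likewise assumed. The change is worth making because it removes an avoidable bias risk and makes the label accurate, not because a material bias has been shown.

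**What to change.** Make these edits together, before the Stage I database lock and without knowledge of unblinded results:

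- In SAP 9.2 and Protocol 11.1, define ITT as all randomized patients analysed by assigned arm. Keep the dosing condition for the Safety set.
- In Protocol 11.4.1, start the primary endpoint clock at randomization, as SAP 9.3 already does.
- In SAP 9.3, define Baseline for undosed patients as the last valid value before randomization.
- In SAP 10.6.1, state that undosed patients are followed to Day 28 where possible, and which of the existing censoring rules applies to those who are not.

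The cost is a few short text edits and slight dilution of the effect. No new type of assessment is needed, the planned 780 is unchanged, and power is about 0.81 at 1% undosed and 0.80 at 2%, at the 0.05 level used for planning.
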